10. STATISTICAL ANALYSIS

10.1 Sample size

The sample size of 45 patients (with potentially a maximum of five teeth per patient) is not based on statistical power considerations, but as a number of patients that will enable useful data to be collected on the functionality and safety of the Calcivis System for assessing the activity of post-Orthodontic lesions. In addition the data may be used to support the design of future clinical studies.

Therefore, it is intended to recruit a total of 45 patients to the study, who have at least one tooth with a visible caries lesion on debond who will be followed up for 12 weeks.

It is expected that up to 100 patients may have to be recruited and imaged with the Calcivis System at de-bond (baseline), in order to find 45 patients with active lesions.

10.2 Statistical Analysis

General Considerations

The planned statistical analysis will be fully described in a Statistical Analysis Plan, which will be finalised prior to the locking of the study database.

The statistical analysis will be performed using SAS version 9.2 or higher.

Analysis Populations

All patients on whom the Calcivis System is used will be included in the Safety Population. This population will be used for all summaries.

For each subject the percentage of teeth showing luminescence using the Calcivis System will be calculated. This will then be summarised over all subjects for each post-baseline visit. Additionally the percentage of teeth showing luminescence will be summarised for each post-baseline visit by Investigator and ICDAS score at Visit 1.

For each subject the percentage of teeth with each ICDAS score will be calculated. This will then be summarised over all subjects for each post-baseline visit. The ICDAS score will also be cross-tabulated with the presence / absence of luminescence from individual teeth for each visit.

User and Patient questionnaires will be summarised descriptively for each visit.

Adverse events during the course of the study will also be summarised descriptively.

Missing Data

Missing data will not be imputed.

Interim Analysis

An interim report of the study may be produced before all patients have completed the study. Since there is no statistical testing being performed, no adjustments to the statistical analysis are required due to any interim report.

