Inclusion and Exclusion Criteria	
Inclusion criteria
 
 1. Patient must be \geq 12 years old 2. Patient must have had orthodontic appliances placed on the upper incisors and / or canines for at least 12 months, and be ready for de-bond 3. Patient must have at least one, active white spot lesion identified by the Calcivis System immediately post de-bond 4. Patient and / or parent or guardian must be willing and able to give written informed consent 5. Patient and / or parent or guardian must be willing and able to adhere to study schedule 
Exclusion criteria
 
 1. Any Patient with recent tooth bleaching (within previous two weeks of imaging with the Calcivis System) or within the follow-up period 2. Any patient currently taking part in a clinical research study, or who has taken part in a clinical research study in the previous three months 3. Pregnant and / or nursing mothers
Control	There will be no Control teeth for this study
Number of Patients	Up to 100 patients may have to be recruited, to obtain 45 eligible patients for follow-up

Statistical Rationale	
The sample size of 45 patients (with potentially a maximum of five teeth per patient) is not based on statistical power considerations, but as a number of patients that will enable useful data to be collected on the functionality and safety of the Calcivis System for assessing the activity of post-Orthodontic lesions. In addition the data may be used to support the design of future clinical studies.
 
The percentage of teeth showing luminescence using the Calcivis System will be summarised for each post-baseline visit. Additionally the percentage of teeth showing luminescence will be summarised for each post-baseline visit by Investigator and ICDAS score at Visit 1.
 
For each subject the percentage of teeth with each ICDAS score will be calculated. This will then be summarised over all subjects for each post-baseline visit. The ICDAS score will also be cross-tabulated with the presence/absence of luminescence from individual teeth for each visit.
 
User and patient questionnaire data will be summarised descriptively for each visit.
 
Adverse events during the course of the study will also be summarised descriptively.
 
All patients on which the Calcivis System was used at least once will be included in all analyses.

Number of Sites	One (1)

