8.2 Study Visit 1 – de-bond - baseline

At this visit, written Informed Consent (ref. 15.3) will be taken by the Investigator and the following information collected and procedures carried out.

Pre-Imaging Information collected

Demographics – DoB and gender

Relevant medications – calcium supplements and antacids

Oral hygiene information – routine brushing regime, toothpaste and any other dental products used

Orthodontic history – date braces applied, type of bracket, ligation used, and any other relevant information (e.g. re-mineralization products used)

Preparation of the Calcivis System

The Calcivis System must be prepared according to the manufacturer's Instructions For Use. Single-use Disclosing Solution (Photoprotein) should not be reconstituted more than 2 hours before the first tooth is imaged. Once reconstituted, the multi-use vial of Disclosing Solution (Photoprotein) should be stored at 2 to 8^o, up to a maximum of 2 weeks.

Teeth Preparation Procedure

Immediately after the appliances have been removed, up to a maximum of four teeth from any of the four upper incisors and two canines with visible white spot lesions on de-bond, will be identified and recorded for assessment using the Calcivis System.

Each free smooth surface will be air dried before taking close-up colour photographs of the tooth or teeth with a digital camera for reference, and coded for ICDAS (1,2 or 3).

All relevant teeth will then be cleaned by the Orthodontist, by brushing with water, and rinsing with water and an air-water spray from a conventional dental 3-in-1 device, according to the Tooth Cleaning Protocol (Appendix 2). Patients will be asked to rinse out thoroughly with tap water.

Imaging with the Calcivis device

Extreme care must be taken to ensure the surface of the tooth and surrounding area are free from saliva before imaging with the Calcivis System by air drying for a minimum of 10 seconds immediately before application of the disclosing solution and Calcivis System imaging.

Images of the free smooth tooth surfaces, will be taken with the Calcivis System according the Instructions For Use. If the first image of a selected tooth is not clear, it is acceptable to take a second image of the selected tooth, however patients must rinse out with water before the subsequent image

can be taken, and the tooth air-dried as described above. A maximum of four images per patient can be taken with the Calcivis System.

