Immediately after all imaging has been completed, patients will be asked to rinse out with tap water.

Any adverse events observed or volunteered by the patient will be recorded.

The images generated with the Calcivis System will be stored digitally on the laptop provided. The software overlays the two sets of images (before and after application of the disclosing solution), resulting in a demineralization map of each imaged tooth.

At the end of the imaging procedures, the Investigator will review the images on the laptop and record any 'activity' as a YES or NO, according to areas of elevated bioluminescence. If there is no area of elevated bioluminescence on a selected tooth surface, that tooth will not be followed up at future visits. Only patients with at least one tooth surface showing areas of active demineralization will be followed up.

In the event that none of the teeth imaged from a patient show any active demineralization, that patient will be withdrawn from the study and will be replaced.

At the end of Visit 1, the Investigator will share the images of the teeth with the patient and discuss the results.

The Calcivis System will be dismantled and cleaned according to the Instructions For Use and all consumables will be disposed according to the Instructions For Use.

Representatives of the Sponsor, Calcivis Ltd, will be available throughout Visit 1 and any subsequent visits, to provide technical support for the use of the Calcivis System, as and when required. Consent will be sought from the patient and / or parent or guardian.

Patients will then resume routine procedures carried out at de-bond. Patients will be advised to follow a routine tooth brushing / oral hygiene regime of brushing teeth at least twice per day with a fluoride toothpaste, taking care to brush any areas highlighted by the orthodontist, and to use a mouthwash at different times of the day from brushing.

Post-Imaging Questionnaires

At the end of the imaging procedures, patients will be asked to remain at the Orthodontic clinic to complete a Patient Questionnaire. Visit 1 is then complete.

In addition, at the end of each baseline study visit, the Investigator and Dental Nurse will each complete relevant sections of a User-Questionnaire

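### Does the synopsis define the luminescence percentage differently from Section 10.2 by leaving out the per-subject step?

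*Protocol*

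**What the plan says.** The primary objective (protocol, Section 4.1) is measured by presence or absence of bioluminescence from de-bond to 8 weeks. Its descriptive summary is the percentage of teeth luminescent at each post-baseline visit.

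- **Section 10.2:** "For each subject the percentage of teeth showing luminescence using the Calcivis System will be calculated". Then: "This will then be summarised over all subjects for each post-baseline visit".
- **Synopsis, Statistical Rationale:** "The percentage of teeth showing luminescence using the Calcivis System will be summarised for each post-baseline visit". No per-subject step appears here, but the next paragraph writes that step out for the caries score: "For each subject the percentage of teeth with each ICDAS score will be calculated".
- **Both places** also plan a table at tooth level. In Section 10.2 it reads: "The ICDAS score will also be cross-tabulated with the presence / absence of luminescence from individual teeth for each visit".
- **Both places** add a breakdown of the luminescence percentage by Investigator and by Visit 1 ICDAS score, in the same short form and with no unit stated.

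The number of teeth per patient varies. Section 8.2 selects "up to a maximum of four teeth from any of the four upper incisors and two canines", drops teeth that are inactive at baseline, and states: "Only patients with at least one tooth surface showing areas of active demineralization will be followed up". A followed patient therefore contributes one to four teeth.

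**The concern.** The two statistical texts are otherwise almost identical, so a missing clause in one of them stands out. The synopsis spells out the per-subject step for ICDAS and not for luminescence. A careful reader could conclude that the contrast is meant: ICDAS by patient, luminescence by tooth.

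The unit matters in principle. A mean of per-subject percentages gives each patient equal weight, whereas a pooled percentage gives each tooth equal weight, so patients with four teeth count four times as much as those with one. The figure concerned describes the primary objective. Section 10.2 also allows an interim report before all patients have finished, while the SAP need only be final before database lock. If the unit really were open, it could be chosen after some results had been seen.

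**Working it through.** **1. Do the texts conflict?** The protocol states no figure to reproduce: the 45 patients have no power basis, no test is planned and no luminescence rate is assumed. The first check is therefore on wording.

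- The synopsis names the quantity (percentage of teeth luminescent) and the time points. It does not say that teeth are pooled over patients.
- Section 10.2 names the same quantity and time points and adds how it is calculated.
- Immediately afterwards, Section 10.2 introduces its breakdown by Investigator and ICDAS score with nearly the synopsis wording, again without the per-subject step. The short phrase therefore does not by itself signal a pooled estimate.

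The synopsis is less specific than Section 10.2 but compatible with it.

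**2. Is the definition still open when an interim report is written?** The Revision History shows that version 5 introduced the interim provision. The per-subject definition stands in that same version, so it does not wait for the SAP.

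**3. How far apart could the two readings be?** For patient i with m_i followed teeth, of which x_i are luminescent, n patients and T = Σm_i teeth:

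- per-subject mean = (1/n) Σ(x_i/m_i)
- pooled percentage = Σx_i / T

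The protocol supplies n = 45 and one to four teeth. Everything else is assumed: persistence p of 20%, 40% or 60%; within-patient correlation (ICC) 0, 0.3 or 0.5; and two tooth-count mixes for 1/2/3/4 teeth, namely equal (25% each, about 112.5 teeth) and skewed (50/20/15/15%, about 87.7 teeth).

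*Persistence unrelated to tooth count.* Both readings then have expectation p, so the expected gap is zero. With ICC 0 the variance of the gap is approximately p(1−p) × [mean(1/m)/n − 1/T]. For the equal mix at p = 0.2:

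- mean(1/m) = (1 + 0.5 + 0.333 + 0.25)/4 = 0.521
- variance = 0.16 × (0.521/45 − 1/112.5) = 0.00043, so SD = 0.0207
- mean absolute gap ≈ 0.80 × 0.0207 = 0.017; 95th percentile ≈ 1.96 × 0.0207 = 0.041

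The simulation (20,000 runs per setting) gave 0.016 and 0.040 there. Over all 18 settings it gave:

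| Quantity | Range |
|---|---|
| Mean signed gap | within 0.05 points of zero |
| Mean absolute gap | 1.6 to 2.9 points |
| 95th percentile of absolute gap | 4.0 to 7.1 points |
| Studies with a gap above 5 points | about 2% to 17% |
| Standard error of the per-subject mean | 4.3 to 6.7 points |

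At the low end the ratio of mean gap to standard error is 1.6/4.3 = 0.37; at the high end it is 2.9/6.7 = 0.43.

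*Persistence varying with tooth count.* Take 15, 12, 9 and 9 patients with 1, 2, 3 and 4 teeth (15 + 24 + 27 + 36 = 102 teeth):

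| Persistence at 1/2/3/4 teeth | Per-subject mean | Pooled |
|---|---|---|
| 40/40/40/40% | 40.0% | 40.0% |
| 35/40/45/50% | 18.6/45 = 41.3% | 45.0/102 = 44.1% |
| 20/35/50/65% | 17.55/45 = 39.0% | 48.3/102 = 47.4% |
| 65/50/35/20% | 20.7/45 = 46.0% | 38.4/102 = 37.6% |

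A gap of about 8 points therefore needs a steep gradient, and the protocol gives no ground for assuming one. Contrived cases can go further. If 22 patients have one tooth, none luminescent, and 23 have four teeth, all luminescent, the figures are 23/45 = 51.1% and 92/114 = 80.7%. If all patients have the same number of teeth, the two readings coincide.

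**The case for a change.** The strongest argument for a change is that the protocol states the summary of its primary measure twice, and not in the same way. The synopsis applies the per-subject step to ICDAS in the very next paragraph, so its absence for luminescence may be deliberate. The Revision History records no edit that explains the difference. In up to about one simulated study in six, chance alone separates the two figures by more than 5 points, and the sponsor intends the data to inform later studies. The repair would cost one sentence.

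The textual difference stands, and so do the simulated gaps. The inference that the unit is unsettled does not. It treats a drafting contrast within a synopsis as a competing definition, although the analysis section defines the figure in full, puts it first, and introduces the tooth-level table only as an addition. Choosing the unit after an interim look would mean setting aside Section 10.2. Which table is labelled main and which supportive is ordinary SAP content, and the SAP is not at hand.

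One loose end is real but equally minor: neither place gives the unit for the breakdown by Investigator and Visit 1 ICDAS score. Since that score belongs to a tooth, grouping teeth by score is the natural reading, and an analyst would settle it in the table specifications.

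**Conclusion.** This is a clerical mismatch, and no change to the plan follows. The synopsis abbreviates a summary that Section 10.2 defines clearly, and following Section 10.2 gives a sound description of the primary measure.

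That conclusion rests on the wording and does not depend on the size of the gap. The size supports it: with persistence unrelated to tooth count, the expected difference is zero and the chance difference averages 1.6 to 2.9 points, within the sampling error of the estimate. These figures depend on assumed persistence rates, tooth-count mixes and correlations. A difference near 8 points would need persistence to change steeply with tooth count, which the protocol neither states nor supports. Even then, Section 10.2 would decide which figure to report, and the planned ICDAS-by-luminescence table would largely show the tooth-level one.

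No test, power calculation or decision threshold depends on the point, and no planned output is lost. Repeating the two sentences of Section 10.2 in the synopsis at the next revision would make the text tidier but would alter no result.

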11. DATA MANAGEMENT

All data collected on the Case Report Forms will be 100% verified against source data (Patient's Dental / Medical Records and Source Document Worksheets) by the monitoring staff. The data from the CRFs will be entered on to a validated Database. Quality control of the data entry process will be performed and any resulting discrepancies adjudicated against the CRFs. The data will then be subjected to validation checks and any resulting Data Queries will be resolved at site with the assistance of the monitoring staff. Once all Data Queries are resolved, critical data will be 100% verified (including adverse events), comparing the Database against the CRF.

The database will then be locked and the study data prepared for statistical analysis.

Any data existing for patients who withdraw voluntarily or are withdrawn from the study, will be used in the study analysis, unless the patient states this is contrary to their wishes.

Details of the data to be presented will be outlined in the Statistical Analysis Plan.

12. STUDY DATA REPORTING AND STUDY REPORT

A final Clinical Study Report of the results will be compiled by Calcivis Ltd which will be approved and signed off by each participating Investigator. A copy will be made available to each Investigator. In addition, a lay summary report of the clinical study results will be produced and made available for any patients who request a copy.

Copies of the final Clinical Study Report will be provided to the Research Ethics Committee, NHS R & D and any other local approvers.

13. PUBLICATION OF RESULTS

Calcivis Ltd commits to communicating or otherwise making available for public disclosure the results of the study regardless of the outcome. Public disclosure includes publication of a paper in a scientific journal, abstract submission with a poster or oral presentation at a scientific meeting, or by other means.

At the end of the study, one or more manuscripts for publication will be prepared in collaboration between all Investigator(s) and Calcivis Ltd on the collective study results. Calcivis Ltd will not suppress or veto publications, however Calcivis Ltd reserves the right to postpone publication and / or communication for 180 days to protect intellectual property.

Any subsequent publications, (journal submissions, posters, white papers, marketing literature etc) will be covered in a separate Publication Strategy document provided by Calcivis Ltd.

Calcivis Ltd will register this clinical study on www.clinicaltrials.gov website and report the study results accordingly.

14. REGULATORY, ADMINISTRATIVE AND CONTRACTUAL INFORMATION

14.1 Sponsor's Responsibilities

The Sponsor, (Calcivis Ltd) is responsible for providing Investigators with the information and training they need to conduct the clinical study properly and in accordance with the Clinical Study Plan. The Sponsor must ensure proper monitoring of the Clinical Study, that Research Ethics Committee approval, NHS, R & D approval and any other required local approvals are obtained and remain current, and that the Research Ethics Committee, NHS, R & D and other local approvers are informed of significant new information about the clinical study as required.

This information should include the following:

- A current signed copy of the Clinical Study Plan and any amendments
- A signed copy of the signed Clinical Investigation Agreement or equivalent Contract - for each participating Investigator / Site
- All information pertaining to Research Ethics Committee review and approval of this clinical study including a copy of the REC Letter of Favourable Opinion and a blank copy of the approved Patient Information / Consent Form for all sites involved.
- All information pertaining to NHS, R & D or other local approvals / notifications of this clinical study including a copy of the approval letter for each site.
- Copies of current signed and dated Curriculum Vitae's of the Investigator and all relevant site personnel

14.2 Amendments

Any change or addition to this Clinical Study Plan requires a written amendment which must be approved by the Sponsor before the change or addition can be considered effective. Where Research Ethics Committee approval is required, the Principal Investigator must submit the appropriate

documentation to the main REC, and obtain written approval for the amendment before it can be implemented at the investigative site(s). A copy of the written approval must be provided to the Sponsor. All Investigators must submit relevant documentation to each site's NHS, R & D or other relevant local approver and obtain approval before the Amendment can be implemented. Copies of the written approvals must be submitted to the Sponsor. Amendments will be circulated promptly to all investigators by the Sponsor.

14.3 Deviations

A Deviation is a failure to comply with the requirements specified within this Clinical Study Plan without adequate justification. Examples of deviations may include enrolment of a study patient who does not meet all of the inclusion / exclusion criteria specified in the Clinical Study Plan, or missed study visits without adequate documentation.

All deviations must be documented on the appropriate forms and reported to the Sponsor. All deviations will be reviewed and assessed for their impact on patient safety by Calcivis Ltd.

The investigators shall conduct this Clinical Study in accordance with this Clinical Study Plan and any conditions of approval / notification imposed by the Research Ethics Committee, NHS, R & D and / or other local approvers. Failure to comply with and / or inability to meet these regulations may jeopardise further participation of the Investigator or Investigative Site in this and future clinical studies.

14.4 Monitoring Procedures and Source Documents

A clinical monitor will be appointed by the Sponsor for each investigative site. The monitor is responsible for assessing the Investigator's compliance with the Clinical Study Plan and for performing Source Document Verification. The monitor is also responsible for reporting to the Sponsor on the progress of the Clinical Study.

Source documents include all information, original records of clinical findings, observations, or other activities in a clinical study necessary for the reconstruction and evaluation of the study e.g patient's dental / medical records, clinical charts, laboratory reports, photographs, patient diaries or questionnaires, device accountability records, recorded data from automated instruments, copies or transcriptions certified after verification as being accurate and complete, and any certification from medico-technical departments involved in the clinical study.

At the Site Initiation Visit the monitor will review the Clinical Study Plan, Case Report Forms and all associated study documentation and procedures with the Investigator and study personnel. During the course of the study, the monitor will maintain regular contact with the investigative site and conduct on-site monitoring visits and source data verification on a regular basis to ensure compliance with this Clinical Study Plan. The number and frequency of the visits for each site, will be determined by the rate of patient recruitment. During monitoring visits the monitor will require access the patient dental / medical records in order to carry out source document verification to ensure all data recorded in the study records is accurate and complete and the data can be submitted to the Sponsor in a timely manner and to verify that the investigative site facilities continue to be adequate. Throughout the

study the monitor must check that all adverse events have been collected, recorded and reported as required and discuss the implication of all Serious Adverse Events with the site Investigator.

The Investigator must set aside a reasonable amount of his / her time for these visits and the time of any relevant site personnel.

